5.4.2 Reporting Requirements for Serious Adverse Events and Adverse Events of Special Interest

5.4.2.1 Events That Occur prior to Study Drug Initiation

After informed consent has been obtained but prior to initiation of study drug, only serious adverse events caused by a protocol-mandated intervention should be reported. The Serious Adverse Event/Adverse Event of Special Interest Reporting Form provided to investigators should be completed and submitted to the Sponsor or its designee immediately (i.e., no more than 24 hours after learning of the event), either by faxing or by scanning and e-mailing the form with use of the fax number or e-mail address provided to investigators.

5.4.2.2 Events That Occur after Study Drug Initiation

After initiation of study drug, serious adverse events and adverse events of special interest will be reported until 24 weeks after the last dose of study drug. Investigators should record all case details that can be gathered immediately (i.e., within 24 hours after learning of the event) on the Adverse Event eCRF and submit the report via the electronic data capture (EDC) system. A report will be generated and sent to Roche Safety Risk Management by the EDC system.

In the event that the EDC system is unavailable, the Serious Adverse Event/Adverse Event of Special Interest Reporting Form provided to investigators should be completed and submitted to the Sponsor or its designee immediately (i.e., no more than 24 hours after learning of the event), either by faxing or by scanning and e-mailing the form with use of the fax number or e-mail address provided to investigators. Once the EDC system is available, all information will need to be entered and submitted via the EDC system.

Instructions for reporting post-study adverse events are provided in Section [5.6](#).

5.4.3 Reporting Requirements for Pregnancies

5.4.3.1 Pregnancies in Female Patients

Female patients of childbearing potential will be instructed to immediately inform the investigator if they become pregnant during the study or within 24 weeks after the last dose of study drug. A Clinical Trial Pregnancy Reporting Form should be completed and submitted to the Sponsor or its designee immediately (i.e., no more than 24 hours after learning of the pregnancy), either by faxing or by scanning and e-mailing the form with use of the fax number or e-mail address provided to investigators. Pregnancy should not be recorded on the Adverse Event eCRF. The investigator should discontinue study drug and counsel the patient, discussing the risks of the pregnancy and the possible effects on the fetus. Monitoring of the patient should continue until conclusion of the pregnancy. Any serious adverse events associated with the pregnancy (e.g., an event in the fetus, an event in the mother during or after the pregnancy, or a congenital anomaly/birth defect in the child) should be reported on the Adverse Event eCRF. In addition, the investigator will submit a Clinical Trial Pregnancy Reporting Form when updated information on the course and outcome of the pregnancy becomes available.

5.4.3.2 Pregnancies in Female Partners of Male Patients

Although embryo-fetal development studies are not available, condom use will not be required in male patients enrolled in the study because the margin between the minimal anticipated biological effect level (MABEL) plasma concentration (7 ng/mL) and the estimated maternal C_{max} (at both 1.5 and 3 mg/kg QW dosing regimens) is greater than 10-fold (Banholzer et al. 2012). At this time, very little emicizumab is thought to transfer into semen, and there are no known reproductive risks to female partners of male patients treated with emicizumab, so contraception use by male patients is not required for participation in the study. Therefore, no proactive collection of pregnancy information for female partners of male patients treated with emicizumab will be required.

5.4.3.3 Abortions

Any abortion should be classified as a serious adverse event (as the Sponsor considers abortions to be medically significant), recorded on the Adverse Event eCRF, and reported to the Sponsor immediately (i.e., no more than 24 hours after learning of the event; see Section [5.4.2](#)).

5.4.3.4 Congenital Anomalies/Birth Defects

Any congenital anomaly/birth defect in a child born to a female patient exposed to study drug should be classified as a serious adverse event, recorded on the Adverse Event eCRF, and reported to the Sponsor immediately (i.e., no more than 24 hours after learning of the event; see Section [5.4.2](#)).

5.5 FOLLOW-UP OF PATIENTS AFTER ADVERSE EVENTS

5.5.1 Investigator Follow-Up

The investigator should follow each adverse event until the event has resolved to baseline grade or better, the event is assessed as stable by the investigator, the patient is lost to

follow-up, or the patient withdraws consent. Every effort should be made to follow all serious adverse events considered to be related to study drug or study-related procedures until a final outcome can be reported.

During the study period, resolution of adverse events (with dates) should be documented on the Adverse Event eCRF and in the patient's medical record to facilitate source data verification.

All pregnancies reported during the study should be followed until pregnancy outcome.

5.5.2 Sponsor Follow-Up

For serious adverse events, adverse events of special interest, and pregnancies, the Sponsor or a designee may follow up by telephone, fax, electronic mail, and/or a monitoring visit to obtain additional case details and outcome information (e.g., from hospital discharge summaries, consultant reports, autopsy reports) in order to perform an independent medical assessment of the reported case.

5.6 ADVERSE EVENTS THAT OCCUR AFTER THE ADVERSE EVENT REPORTING PERIOD

The Sponsor should be notified if the investigator becomes aware of any serious adverse event that occurs after the end of the adverse event reporting period (defined as 24 weeks after the last dose of study drug or rollover to an extension study), if the event is believed to be related to prior study drug treatment.

These events should be reported through use of the Adverse Event eCRF. However, if the EDC system is not available, the investigator should report these events directly to the Sponsor or its designee, either by faxing or by scanning and e-mailing the Serious Adverse Event/Adverse Event of Special Interest Reporting Form with use of the fax number or e-mail address provided to investigators.

5.7 EXPEDITED REPORTING TO HEALTH AUTHORITIES, INVESTIGATORS, INSTITUTIONAL REVIEW BOARDS, AND ETHICS COMMITTEES

The Sponsor will promptly evaluate all serious adverse events (see Section [5.2.2](#)) and adverse events of special interest (see Section [5.2.3](#)) against cumulative product experience to identify and expeditiously communicate possible new safety findings to investigators, IRBs, ECs, and applicable health authorities based on applicable legislation.

To determine reporting requirements for single adverse event cases, the Sponsor will assess the expectedness of these events using the following reference document:

- RO5534262 (Emicizumab) Investigator's Brochure

The Sponsor will compare the severity of each event and the cumulative event frequency reported for the study with the severity and frequency reported in the applicable reference document.

Reporting requirements will also be based on the investigator's assessment of causality and seriousness, with allowance for upgrading by the Sponsor as needed.

6. STATISTICAL CONSIDERATIONS AND ANALYSIS PLAN

No formal hypothesis testing is planned for this study. All analyses will be descriptive. The 6 run-in patients will be analyzed separately from the expansion cohort.

6.1 DETERMINATION OF SAMPLE SIZE

The sample size of 6 patients for the PK run-in cohort is considered appropriate to assess pharmacokinetics and safety to allow for an informed decision to open the subsequent expansion cohort with 40 additional patients.

The overall sample size of 40 patients in the expansion cohort is based primarily on clinical considerations taking into account the limited number of patients with hemophilia A. A sample size of 40 patients is expected to provide statistically robust point estimates with meaningfully narrow confidence intervals.

6.2 SUMMARIES OF CONDUCT OF STUDY

The number of patients who enroll, discontinue, or complete the study will be summarized. Reasons for premature study withdrawal will be listed and summarized. Enrollment and major protocol deviations will be listed and evaluated for their potential effects on the interpretation of study results.

6.3 SUMMARIES OF DEMOGRAPHIC AND BASELINE CHARACTERISTICS

Demographic and baseline characteristics (including age, sex, etc.) will be summarized using means, standard deviations, medians, and ranges for continuous variables and proportions for categorical variables, as appropriate.

6.4 EFFICACY ANALYSES

The efficacy objective is to evaluate the clinical effect of 6 mg/kg emicizumab Q4W based on the number of bleeds over time.

6.4.1 Efficacy Endpoints

The key efficacy objective is to characterize the efficacy of 6 mg/kg emicizumab Q4W based on the number of bleeds over time for patients in the expansion cohort.

The analyses will be performed using a negative binomial regression model, which accounts for different follow-up times, with the patient's number of bleeds as a function of the time that each patient stays in the study included as an offset in the model.

The number of bleeds will be also annualized (Annualized Bleeding Rate—ABR) for each patient using the following formula:

$$ABR = \left(\frac{\text{Number of bleeds during the efficacy period}}{\text{Total number of days during the efficacy period}} \right) \times 365.25$$

In case the negative binomial model does not converge the above formula will be used as the sole method of analysis.

The clinical effect of prophylactic emicizumab on the number of bleeds, joint bleeds, target joint bleeds, spontaneous bleeds and all bleeds (i.e., those treated and untreated with coagulation factors) over time will be evaluated (see Section 2.2.1).

The number of bleeds, sites of bleeds, and types of bleeds will be summarized for all patients and listed for each patient individually. Several exploratory analyses will be conducted to characterize the type, location, duration, frequency, and pattern of bleeds. For continuous endpoints, descriptive statistics will be calculated and categorical endpoints will be characterized through frequency tables.

The primary final analysis will be performed 24 weeks after the last enrolled patient started treatment or has withdrawn prematurely, whichever occurs first.

A detailed description of the statistical methods that will be used for the efficacy analyses will be provided in the Statistical Analysis Plan.

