The number of bleeds, sites of bleeds, and types of bleeds will be summarized for all patients and listed for each patient individually. Several exploratory analyses will be conducted to characterize the type, location, duration, frequency, and pattern of bleeds. For continuous endpoints, descriptive statistics will be calculated and categorical endpoints will be characterized through frequency tables.

The primary final analysis will be performed 24 weeks after the last enrolled patient started treatment or has withdrawn prematurely, whichever occurs first.

Safety Analyses

The safety analyses population will be based on all patients who received at least one administration of emicizumab. Safety will be assessed through descriptive summaries of adverse events, laboratory test results (serum chemistry and hematology including complete blood count with differential and platelet counts), ECGs, vital signs, anti-drug antibodies (ADAs), and de novo anti-FVIII inhibitors.

To evaluate the overall safety of emicizumab, the incidence of adverse events will be summarized and presented by System Organ Class mapped term, appropriate thesaurus level, and toxicity grade.

For clinical laboratory data, summary statistics will be presented. In addition, shift tables describing changes from baseline will be presented using the WHO toxicity grading scale.

Pharmacokinetic Analyses

PK Run-In Cohort

PK parameters of emicizumab will be estimated using non-compartmental methods after the first and the sixth injections and include:

- T_{max} : Time to maximum observed plasma concentration
- C_{max} : Maximum observed plasma concentration
- AUC_{τ} : Area under the plasma concentration–time curve over a dosing interval
- AUC_{0-inf} : Area under the plasma concentration–time curve between time zero (predose) extrapolated to infinity (only for the first injection)
- $t_{1/2}$: Apparent terminal half-life
- CL/F and CL_{ss}/F : Apparent Clearance

Concentration data and calculated PK parameters for emicizumab will be presented in individual listings, summary tables (including descriptive statistics: mean, geometric means, medians, ranges, standard deviations, and coefficients of variation) and graphs (including concentration versus time plots on linear and semi-logarithmic scales) as appropriate.

Expansion Cohort

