3.1.2 Expansion Part

An expansion phase will be conducted to further investigate the efficacy, pharmacokinetics, safety, and pharmacodynamics in a cohort of 40 patients. These patients will start with loading doses of 3 mg/kg QW \times 4, followed by a maintenance dose of 6 mg/kg Q4W for at least 24 weeks overall. These patients will undergo PK sampling to investigate trough concentrations (C_{trough}) and samples (predose) will be drawn as per the schedule of assessments (see [Appendix 2](#)).

Figure 1 Study Schema

PD=pharmacodynamic; PK=pharmacokinetic; Q4W=every 4 weeks.

^a Analysis will occur when last patient enrolled in the PK run-in cohort has been in the study for 6 weeks.

The primary analysis (descriptive analyses of the study objectives) will be conducted either after the last enrolled patient completes the 24-week treatment period, is lost to follow-up, or has withdrawn, whichever occurs first.

During the study, individual bleeds will be captured as they occur while HRQoL, health status, patients' preference and days of school or work missed will be assessed as outlined in the schedule of assessments in protocol. Patients (or their legally authorized representative) will be asked on a weekly basis to record via their electronic, handheld device whether a bleed has occurred and whether treatment for a bleed or treatment to prevent a bleed has been given.

Physical examinations, vital signs, ECG, and laboratory assessments will be performed as detailed in the schedule of assessments (see [Appendix 1](#)) and will be the same for all patients receiving emicizumab, regardless of whether they are enrolled in the PK run-in cohort or the expansion cohort. Adverse events will be captured on an ongoing basis, as they occur during the study.

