The primary efficacy analysis will be conducted after all enrolled patients complete the 24-week treatment period, are lost to follow-up, or have withdrawn. The primary analysis will only consist of descriptive analyses of the objectives with no formal hypothesis testing.

An interim analysis for Study BO39182 may be conducted to support regulatory submissions and an interim clinical study report (CSR) may be written.

After 24 weeks of prophylactic treatment with emicizumab, all patients will be provided with the option to up-titrate their dose to 3 mg/kg QW, if they meet protocol-defined criteria of suboptimal response (see Section 4.3.2.1 of the protocol). Thereafter, the patient may choose to down-titrate to 6 mg/kg Q4W, 3 mg/kg Q2W, or 1.5 mg/kg QW; subsequent up-titration would again be allowed if protocol-defined criteria were met.

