2.3 OBJECTIVES AND ENDPOINTS

2.3.1 Efficacy Period for All Endpoints

The start of the efficacy period for each individual patient is defined as the date of first emicizumab administration.

The end of the efficacy period is defined as the date of the clinical cutoff or the date of withdrawal from the initial study period (i.e., treatment phase according to eCRF-Subject Disposition page), whichever is earlier. For patients whose dose is up-titrated, the efficacy period ends a day prior to the first day on the up-titrated dose.

The efficacy period on a given up-titrated/down-titrated dose starts with the first day on this dose and ends on the date of the clinical cutoff or the date of withdrawal or date preceding the next up-titration/down-titration. Bleeds on the up-titrated/down-titrated dose are analyzed separately (see Section [4.1](#)).

Bleed rate is defined as the number of bleeds over the efficacy period. A bleed is counted in the primary analysis if it was treated with coagulation factors and fulfills the adapted International Society on Thrombosis and Haemostasis (ISTH; [Blanchette et al. 2014](#)) criteria, as described in Section 4.5.8 of the protocol. More specifically, the rules outlined in the sections below are applied.

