2.5 ANALYSIS TIMING

Analysis on the PK run-in cohort will be conducted 6 weeks after the first 6 patients have completed 6 weeks in the study. This analysis will focus on pharmacokinetics and safety to inform on the opening of the expansion cohort.

The primary analysis will take place at the earliest time when all enrolled patients in the expansion cohort complete 24 weeks in the study or have withdrawn. These analyses will be carried out separately for patients in the expansion cohort and the PK run-in cohort.

The final analysis will occur at the end of the study as defined in the protocol. Additional updates may be performed between the primary and final analyses, as requested by Health Authorities or deemed necessary by the Sponsor.

Additional analyses for Study BO39182 may be conducted to support regulatory submissions.

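### The protocol lets the last enrolled patient's early departure trigger the primary analysis, whereas the SAP waits for every patient to complete 24 weeks or leave

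*Protocol*

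**What the plan says.** The protocol states the timing of the primary analysis four times.

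- **Section 3.1.2 and the synopsis design text:** the analysis is conducted "after the last enrolled patient completes the 24-week treatment period, is lost to follow-up, or has withdrawn, whichever occurs first".
- **Section 6.4.1 and the synopsis statistical text:** it is performed "24 weeks after the last enrolled patient started treatment or has withdrawn prematurely, whichever occurs first".

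All four refer to one person, the last enrolled patient. None adds that the other patients must have reached 24 weeks.

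The SAP body states a different rule twice.

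- **Section 2:** the primary efficacy analysis is "conducted after all enrolled patients complete the 24-week treatment period, are lost to follow-up, or have withdrawn".
- **Section 2.5, on analysis timing:** it takes place "at the earliest time when all enrolled patients in the expansion cohort complete 24 weeks in the study or have withdrawn".

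The date matters because of SAP 2.3.1: "The end of the efficacy period is defined as the date of the clinical cutoff or the date of withdrawal", whichever is earlier. Up-titration also ends the period. For a patient still on the initial regimen, the cutoff therefore sets both the bleed count and the follow-up time. Protocol 4.6.1 says that expansion-cohort withdrawals are not replaced, so no later patient would reset the clock.

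**The concern.** A trigger that depends on one patient is safe only if that patient stays. By definition the last enrolled patient entered after everyone else, so his or her 24-week date is the latest in the cohort. When the patient completes, everybody has had time to reach 24 weeks. When the patient leaves early, that guarantee goes, and the protocol counts the departure itself as a trigger.

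Two things are then at stake. One is the person-time behind the annualized bleeding rate, on which the protocol's expectation of meaningfully narrow confidence intervals (Section 6.1) depends. The other is the set of 24-week outcomes: quality of life and EQ-5D-5L are scheduled at Week 25 (Day 169), and SAP 4.5.2 reports the proportion with a meaningful change from baseline to Week 24. With two rules in force, the documents also do not define a single cutoff for the same report.

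**Working it through.** The plan gives no figure to reproduce: the cohort size of 40 has no stated precision inputs. The check is a comparison of texts followed by an illustration.

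**Texts compared**

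| Place | Whose status counts | Early departure of the last patient is a trigger? |
|---|---|---|
| Protocol 3.1.2; synopsis, design | Last enrolled patient | Yes, explicitly |
| Protocol 6.4.1; synopsis, statistics | Last enrolled patient | Ambiguous |
| SAP 2 | All enrolled patients | No |
| SAP 2.5 | All expansion-cohort patients | No |

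The 6.4.1 sentence is ambiguous because the 24 weeks can be taken to run from either the start or the withdrawal. On that reading there is no early trigger. Section 3.1.2 does not allow it, since it lists completion, loss and withdrawal as alternatives and takes the earliest.

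**When the rules differ**

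Let the last patient start at week E (first start = 0) and leave at week w. The earliest cutoff under Protocol 3.1.2 is E + w. A patient who started at s then has E + w − s weeks, which is under 24 exactly when E − s < 24 − w. If w = 24, no earlier starter falls short and the rules coincide.

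**Illustration**

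Assumed, and not in the documents: 40 evenly spaced starts, sᵢ = E·i/39 for i = 0 to 39, with no other dropout and no up-titration. Number of the other 39 with under 24 weeks at the protocol cutoff:

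| Last patient leaves at | E = 12 | E = 24 | E = 36 |
|---|---|---|---|
| Week 4 | 39 | 32 | 21 |
| Week 12 | 38 | 19 | 12 |
| Week 20 | 12 | 6 | 4 |
| Week 24 (completes) | 0 | 0 | 0 |

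Two cases in full, both with w = 4 (mean i over the other 39 is 19):

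- **E = 13.** Cutoff at week 17; follow-up is 17 − i/3. The longest is 17 weeks, so 0 of 39 have 24 weeks. Mean = 17 − 19/3 = 10.7 weeks.
- **E = 26.** Cutoff at week 30; follow-up is 30 − 2i/3. This is at least 24 for i = 0 to 9, so 10 of 39 have 24 weeks and 29 do not. Mean = 30 − 38/3 = 17.3 weeks, which is the relevant figure because the efficacy period is not capped at 24 weeks. Capped at 24, it is 17.3 − 30/39 = 16.6.

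**Person-time under the two rules**

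Under the SAP rule the cutoff waits for patient i = 38 to reach 24 weeks.

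- **E = 13.** SAP cutoff at 38/3 + 24 = 36.7, which is 19.7 weeks later. Protocol: 39 × 10.667 + 4 = 420 patient-weeks (8.0 years). SAP: 420 + 39 × 19.667 = 1,187 (22.7 years).
- **E = 26.** SAP cutoff at 76/3 + 24 = 49.3, which is 19.3 weeks later. Protocol: 39 × 17.333 + 4 = 680 patient-weeks (13.0 years). SAP: 680 + 39 × 19.333 = 1,434 (27.5 years).

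If bleeds were Poisson, the standard error of the log rate would be larger under the protocol cutoff by √(1,187/420) = 1.68 and √(1,434/680) = 1.45. Between-patient overdispersion would typically shrink these ratios, because extra time on the same patients then adds less information.

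**The case against.** The strongest reply is that the SAP body already holds the sound rule, in the section devoted to timing, and that Protocol 6.4.1 refers to the SAP for detail. Most of this stands: what is needed is alignment, not redesign. It does not settle the matter, because 6.4.1 refers to the SAP for statistical methods, not for timing, and nothing says which document prevails.

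It is also fair that Section 3.1.2 places the analysis after the event. That sets an earliest time and does not fix a date, so the protocol permits a premature cutoff but does not oblige the sponsor to take it.

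A reader might infer more than the documents support:

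- **That an early departure would catch all the other patients short of 24 weeks.** Only those who started less than 24 − w weeks before the last patient are affected, and the accrual rate is not given.
- **That the efficacy estimate would be biased or error rates inflated.** No hypothesis test is planned, and the negative binomial model has follow-up time as an offset, so unequal follow-up does not invalidate the rates.
- **That data would be lost for good.** Patients may continue beyond 24 weeks, and SAP 2.5 provides for a final analysis and possible updates. The shortfall is at the primary analysis.
- **That the SAP contradicts itself because its Appendix 1 carries the last-patient wording.** That appendix is a copy of the version 2 protocol synopsis, not a second SAP rule.

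The primary analysis may also have been run before protocol version 5, since Section 1.2.2 cites April 2018 data that include this study. The documents do not date the analysis, so this remains an inference.

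**Conclusion.** The inconsistency is real. Protocol 3.1.2 and the synopsis allow one patient's early departure to open the primary analysis, and SAP 2 and 2.5 do not. The rules diverge only if the last enrolled patient leaves before 24 weeks while others are still short of 24 weeks. In that event the cost is less person-time, wider intervals and incomplete Week 25 quality-of-life data at the primary analysis.

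The size depends on accrual and on the week of departure, neither of which is in the documents. In the even-accrual scenarios shown, the number of the other 39 patients with under 24 weeks runs from 4 (36-week accrual, departure at Week 20) to all 39 (12- or 13-week accrual, departure at Week 4). No probability can be put on the last patient leaving early. The point merits correction because the remedy is cheap and leaves one defined cutoff.

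**What to change.** In Protocol 3.1.2, Protocol 6.4.1 and both synopsis statements, replace the trigger with: the primary analysis takes place once every enrolled expansion-cohort patient has completed 24 weeks, been lost to follow-up or withdrawn. This is the SAP 2.5 rule with the loss-to-follow-up term from SAP 2. The term is needed because a lost patient has neither completed nor formally withdrawn.

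Add loss to follow-up to SAP 2.5 as well, and state there that this section governs the timing. Leave SAP Appendix 1 unchanged, as a copy of the version 2 synopsis. If the primary analysis has already been done, record which rule set its cutoff.

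The cost is four wording changes in a protocol amendment and a short SAP clarification. It adds no patients, visits or procedures. If the last patient does leave early, the primary report comes later than the protocol wording would have allowed, by about 19 to 20 weeks in the two Week 4 cases worked in full.
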